#### 12.4.3 Observation Period

✓ ***Day 29 through Day 34***

- No procedures will be performed on these days.
- ❖ Subjects in the **PK Study Sub-Cohort** will remove the Holter on Day 29 approximately 24 hours after it was attached and will be returned by the subject to the site on Day 35.

✓ ***Day 35 Visit***

On Day 35 ( $\pm 2$ ) the following procedures will be performed:

- Adverse event(s) will be recorded
- Concomitant medications documented
- Vital signs: peripheral blood pressure, respiratory and heart rates, and oral temperature will be recorded
- Physical examination
- Local Skin Reaction Score in the Treatment Field
- AK Lesion in the Treatment Field: count (11.1.5) and grading (11.1.1)
- Trial instruction review including appointment for the next visit will be given

The following Procedure will only be performed on the Day 35 Visit in subjects enrolled in the PK Study Sub-Cohort:

❖ PK blood sampling

✓ ***Day 36 through Day 55***

From Day 36 through Day 55 no procedures will be performed.

✓ ***Day 56 Visit***

On Day 56 ( $\pm 4$ ) the following procedures will be performed:

- Adverse event(s): volunteered, elicited, and observed AEs will be recorded
- Concomitant medications documented
- Local Skin Reaction Score in the Treatment Field
- AK Lesions in the Treatment Field: count (11.1.5) and grading (11.1.1)
- Urine pregnancy test will be performed in all females and the results will be recorded
- Photographs of Treatment Field at selected sites
- Trial instruction review including appointment for the next visit will be given

✓ ***Day 57 through Day 83***

From Day 57 through Day 83 no procedures will be performed

✓ ***Day 84 Visit***

On Day 84 ( $\pm 4$ ) the following procedures will be performed:

- Adverse event(s): volunteered, elicited, and observed AEs will be recorded
- Concomitant medications documented
- Local Skin Reaction Score in the Treatment Field
- AK Lesions in the Treatment Field: count (11.1.5) and grading (11.1.1)
- Photographs of Treatment Field at selected sites
- Visit Closure Procedures: Subjects will be thanked for their participation and completion of the study will be noted in the subject's record

**12.5 Unscheduled Visits**

Investigators will invite subjects to attend an unscheduled visit to the investigative site (a) if during the course of the trial a subject's medical condition warrants more frequent observations than prescribed by the clinical protocol and/or (b) if a subject has an AE that has not stabilized or resolved and requires additional visits or follow-up beyond Day 84.

## 12.6 General Restrictions

### 12.6.1 Medication and Other Therapeutic Restrictions

- Topical creams, lotions, makeup or gels of any kind within the selected Treatment Field and the surrounding 2 cm border area from Screening through Day 84 are prohibited unless prescribed by the site Investigator and documented in the subject's file.
- Topical medications within the region of the head that contains the selected Treatment Field (i.e., left face, right face or scalp) are prohibited from Screening through Day 84:
  - Topical skin corticosteroids;
  - Keratolytic-containing therapeutic products or medicated or irritant topical salves, including, but not limited to, alpha-hydroxy acids (e.g., glycolic acid, lactic acid etc. >5%), beta-hydroxy acid (salicylic acid >2%), and urea >5%;
  - Topical retinoids (e.g., tazarotene, adapalene, tretinoin).
- Topical AK treatments including, but not limited to, 5-fluorouracil, diclofenac, imiquimod, or ingenol mebutate, and other at-home AK treatments **at any body site** are prohibited from Screening through Day 84.
- Any AK therapy including, but not limited to, topical medications, cryo-destruction or chemo-destruction, surgical excision, curettage, photodynamic therapy, dermabrasion, chemical peel, or laser resurfacing on the head are prohibited from Screening through Day 84.
- Systemic medications:
  - Immuno-modulatory medications including corticosteroids, interferon or interferon inducers, cytotoxic drugs, or immunosuppressive therapies
  - Retinoid therapy
- Investigation drug or devices.
- Any prescription medications or medicinal products that might obscure, impact, or interfere with proper evaluation of the test product and the Treatment Field are prohibited during the study.
- Starting any new systemic therapy during the trial is prohibited without prior approval of the Study Medical Monitor.

Allowed medications or therapies during the study must be documented and include:

- Subjects taking prescription medication, vitamins, or medical product not specifically prohibited above, may continue taking those products as long as the subject has been taking them continually for at least 2 months prior to Screening with no change in dose, manufacturer, or dosing interval. These medicinal products must be recorded on the appropriate Concomitant Medication pages. All other prescription medications, medicinal products, and vitamins are prohibited without prior approval of the Investigator and the Medical Monitor. The only exceptions to this rule are  $\leq 1000$  mg

acetaminophen,  $\leq 550$  mg naproxen,  $\leq 400$  mg ibuprofen or aspirin 325 mg once daily without prior consultation.

- Intranasal, inhaled, and ophthalmic corticosteroids used in the past for the management of allergies, pulmonary disorders, or other conditions.
- Light bodied bland moisturizer (e.g., Cetaphil, Lubriderm [without alpha-hydroxy acid]) in the selected Treatment Field as an aid to managing AEs with the approval of the site Investigator. Moisturizers must not be applied within six hours of test article application and the Treatment Field must be washed with soap prior to the next dosing.
- Medications used as prn (e.g. bronchodilators, antihistamines, sleep medications) listed as concomitant medications at Screening and/or Day 1 Pre-Dose Visits are permitted.
- Physical AK therapies including, but not limited to, topical cryo-destruction, surgical excision, curettage, dermabrasion, or laser resurfacing on areas other than the head are permitted at any time during the trial.

#### **12.6.2 Topical Product Restrictions**

Subjects should be instructed not to change their soaps, shampoos, laundry detergents, deodorants, etc. from Screening Visit through completion of the Day 84 Visit.

#### **12.6.3 Sun Protection and Tanning**

Subjects must avoid purposeful direct exposure to the sun or ultra-violet light from Screening Visit through completion of the Day 84 Visit activities. Subjects who go outdoors should wear proper clothing and hats that protect their skin from sunlight.

Purposeful tanning and application of tanning agents are prohibited at any time during the trial.

**NOTE:** Subjects should be encouraged to apply sunscreens that the subject has applied previously without developing a reaction. However, no topical sunscreens, creams, lotions, or gels of any kind may be applied within the selected Treatment Field or the surrounding 2 cm border area from Screening through Day 84 unless prescribed by the site Investigator and documented in the subject's file. Therefore, at Screening, subjects should be carefully instructed regarding this restriction as well as use of proper headwear to protect the Treatment Field and the surrounding skin.

#### **12.6.4 Dietary Restrictions**

Subjects may not ingest any product containing jasmine (e.g. jasmine tea).

Subjects may not drink any spiced, herbal, scented, or flavored teas from Screening until completion of all Day 35 procedures since these often contain jasmine without necessarily appearing on the label.

Subjects not included in the PK Study must limit their daily alcohol consumption to  $\leq$  24 ozs (ounces) of beer;  $\leq$  8 ozs of wine; or  $\leq$  2 ozs of any distilled alcoholic beverage from Day 1 through completion of the Day 35 Visit.

Dietary restrictions for the subjects in the PK Study are discussed in Section 12.6.5.

### **12.6.5 Special Restrictions for the PK Study Sub-Cohort**

Subjects enrolled in the **PK Study Sub-Cohort** may not smoke, use nicotine products, or drink any alcohol from the Screening Visit until they complete Day 35 Visit. All medications taken between Screening and Day 84 must be pre-approved by their site Investigator.

### **12.6.6 Physical Exercise Restrictions**

There are no restrictions placed upon physical exercise.

## **12.7 Childbearing Potential**

### **12.7.1 Definitions**

Childbearing Potential: Female subjects with at least one of the following medical conditions will be considered lacking childbearing potential:

- a) aged  $\geq$ 50 years and last normal menstrual period was at least 12 months prior to Screening;
- b) undergone removal of her entire uterus (total hysterectomy); bilateral tubal ligation at least 6 months prior to Screening and/or bilateral oophorectomy

Females who do not meet at least 1 of the above criteria and have that criterion documented in the Medical History will be considered capable of childbearing and must be willing and able to use an acceptable form of contraception. Any subject who considered childbearing and who cannot use an acceptable form of contraception, must be excluded from the study under Exclusion Criterion #3 (Section 8.2).

Acceptable forms of contraception are: a) hormonal contraceptives [e.g., oral, transdermal, injectable, or intravaginal], b) barrier methods [condom and spermicidal or diaphragm/cervical cap and spermicidal], c) partner vasectomy (performed at least six months prior to study entry), or d) total abstinence. Subjects who become sexually active or begin to have relations with a partner who is not sterile during the study must agree to use an effective form of birth control for the duration of the study.

**Urine Pregnancy test:** All women enrolled in the trial must have a negative urine pregnancy test at Screening and Day 1 Pre-Dose. The urine dipstick test must have a minimum sensitivity of 25 mIU for  $\beta$ -hCG/mL.

### **12.7.2 Contraception**

Nursing mothers, pregnant females, and women with childbearing potential (as defined in Section 12.7.1) must be able and willing to use a contraceptive method described in that section, **until 1 month following the final study drug application (i.e., until the Day 56 Visit).**

Non-vasectomized male subjects with female partners without childbearing potential (as defined in Section 12.7.1) are not required to use contraception.

Non-vasectomized male subjects with female partners with childbearing potential (as defined in Section 12.7.1) must agree to use an acceptable form of contraception (as defined in Section 12.7.1) from Screening until 3 months after the last dose of study drug and must refrain from sperm donation for 3 months after the last dose of study drug.

Vasectomized males require no contraception.

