**Treatment Period** – At the **Day 1 Dosing Visit**, subjects will apply the assigned study drug (i.e., active VDA-1102 or placebo) under the supervision of site personnel. Details of the study drug application are found in Section 13.6.

From Day 1 through Day 27 subjects will apply the study each evening approximately 2 hours before bedtime. Site personnel will communicate with the subject once-weekly.

[figure not shown]
On **Day 7** and **Day 14** all subjects will return to the investigative site for safety and efficacy assessments. At each site visit, the subject's study drug will be weighed and the result will be recorded. At each visit, the subject will be re-trained in proper dose application to their Treatment Field. Subjects in the PK Study Sub-Cohort will have a blood sample taken

approximately 12 hours after their evening respective Day 6 and Day 13 evening doses. Subjects in the Nested Phase 1b Safety Sub-Cohort will undergo an additional physical examination, 12-lead ECG, and clinical laboratory assessment on Day 7.

Subjects will return to the site on **Day 28** for safety and efficacy assessments. Subjects in the PK Study Sub-Cohort will undergo blood sampling for analysis at approximately 12, 15, 18, and 21 hours after their Day 27 study drug application. Remaining study drug will be collected from all subjects at this visit.

**Observation Period** – On **Day 35** subjects will return to the site for efficacy and safety assessments. Subjects in the PK Study Sub-Cohort will undergo a single untimed blood sampling. Subjects in the PK Study Sub-Cohort will have a PK sample drawn at the time of their visit. Subjects will return to the sites on Day 56 for efficacy and safety assessments. At the End-of-Study visit on **Day 84**, final efficacy and safety assessments will be performed followed by discharge from the study. Any subject with active TEAE(s) will be followed beyond this scheduled visit until resolution.

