### 8.2 Exclusion Criteria

Subjects fulfilling any of the following criteria will be excluded from study participation:

1. Subject is the PI or any Sub-Investigator, research assistant, pharmacist, Study Coordinator, staff directly involved in the trial, and/or any immediate family member (first degree relative, spouse, adoptees, legal dependents) of any staff directly involved in the trial;
2. Subject has screening results that (a) are clinically significant and have not been approved in writing by the Safety Monitor; (b) suggest an unstable medical condition; (c) preclude the subject's participation out of concern for the subject's safety; or (d) suggest a condition that might confound the subject's data.
3. Subject is: (a) pregnant; (b) lactating; (c) planning to become pregnant during the study, or (d) fertile (as defined in Section 12.7.1) and they or their fertile partner is unable or unwilling to use the contraceptive methods discussed in Section 12.7.2;
4. Subject has any skin pathology, known dermatologic disease, or medical condition that could interfere with the evaluation of the test product or requires the use of an interfering topical or systemic therapy;
5. Subject is immunosuppressed (e.g., organ transplant recipients, HIV, systemic chemotherapy, graft vs. host disease, receiving dialysis, etc.);
6. Subject is currently enrolled in a clinical trial or has received an investigational drug or been treated with an investigational device within 21 days prior to Screening.

7. Subject is unable to comply with the sun protection techniques or the limitations placed on tanning, medicinal products, activities, or foods listed in Section 12.6;
8. Subject has (a) an unstable medical, psychiatric, or social problem; (b) self-reported alcohol or illicit drug dependency; (c) communication or motor deficit; or (d) any similar condition that could place the subject at a safety risk or might interfere with the performance of the trial activities, completion of the trial, and/or interpretation of the subject's data or risk the safety of the subject.
9. Subject may be unreliable for the study including subjects who engage in excessive alcohol intake or drug abuse, or subjects who are unable to return for scheduled follow-up visits.
10. Subject has a known sensitivity to propylene glycol, caprylic acid, dimethyl sulfoxide (DMSO), petrolatum, or paraffin wax.

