### ***Screening Visit***

Subjects will be trained and tested by site personnel at the Screening Visit. The subject will be taught to measure the study drug using placebo tubes supplied by the Sponsor. The subjects will also be taught how to apply the study drug, but they will not use the placebo for this part of the training. In other words, placebo should not be applied to their skin during the training.

Subjects who have difficulty measuring the dose or applying the study drug to the precisely may be asked to bring a dosing partner with them to the Day 1 Pre-Dose Visit. This dosing partner must be willing and able to assist the subject with study drug application once every evening for 28 days.

If the subject (or dosing partner) is unlikely to apply the study drug appropriately, the subject should be terminated from the study based on Inclusion#4 (Section 8.1).

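### Section 12.7.2 equates one month after the last dose with the Day 56 Visit as the end of contraception for women, but the visit window allows that visit only 25 days after the last planned dose

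*Protocol*

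**What the plan says.** Section 12.7.2 of the protocol sets the end of the contraception requirement for women as "until 1 month following the final study drug application (i.e., until the Day 56 Visit". One sentence therefore gives both an interval counted from the last application and a study visit, and presents them as the same thing. The groups it names are "Nursing mothers, pregnant females, and women with childbearing potential". For men to whom the requirement applies, the same section counts from the last dose and attaches no visit.

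Section 12.7.1 contains one further sentence with an end time. It covers "Subjects who become sexually active or begin to have relations with a partner who is not sterile during the study", who "must agree to use an effective form of birth control for the duration of the study". Section 12.3 runs the observation period to Day 84.

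The dates come from elsewhere. Section 7.1 states "From Day 1 through Day 27 subjects will apply the study each evening", and Table 5 and Section 12.4.2 also end home dosing on Day 27. Table 5 and Section 12.4.3 give the Day 56 Visit a window of plus or minus 4 days. Inclusion Criterion 2 and Exclusion Criterion 3 send sites to these contraception sections. Exclusion Criterion 3 also bars a woman who is pregnant or nursing: "Subject is: (a) pregnant; (b) lactating; (c) planning to become pregnant during the study".

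**The concern.** The parenthesis in Section 12.7.2 replaces a fixed interval with a visit whose date can move by four days either way. A site that follows the parenthesis may release a woman before the interval in the same sentence has passed. A site that follows the interval may have to continue past the visit. The protocol does not say which governs.

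The sentence in Section 12.7.1 adds a later end for one group of subjects, and Section 12.7.2 does not acknowledge it. This rule protects participants and is used when eligibility is explained to them, so it should give the same answer however it is read.

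**Working it through.** **Inputs**

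- Last planned dose: evening of Day 27 (Sections 7.1 and 12.4.2, Table 5).
- Day 56 Visit: Day 56 − 4 = 52 to Day 56 + 4 = 60, which is 60 − 52 + 1 = 9 permitted days (Table 5, Section 12.4.3).
- End of study: Day 84 (Section 12.3).
- Length of one month: not defined for contraception. I assume *m* = 28, 29, 30 or 31 days and show all four.

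**The plan's own equation.** On the nominal schedule the visit falls 56 − 27 = 29 days after the last dose. The equation then holds to within about a day for a month of 28 to 30 days, and to two days for a month of 31.

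**Across the window.** The gap is 52 − 27 = 25 days at the earliest and 60 − 27 = 33 days at the latest. A visit on day *v* is too early when *v* − 27 < *m*. The number of permitted days that are too early is therefore 27 + *m* − 52 = *m* − 25.

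| Assumed month (days) | Month reached on | Visit days too early | Count of 9 | Shortfall at a Day 52 visit |
|---|---|---|---|---|
| 28 | Day 55 | 52–54 | 3 | 3 days |
| 29 | Day 56 | 52–55 | 4 | 4 days |
| 30 | Day 57 | 52–56 | 5 | 5 days |
| 31 | Day 58 | 52–57 | 6 | 6 days |

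Days 52, 53 and 54 are too early in every row. The 29-day row is the one implied by the protocol's own parenthesis, because it takes the nominal Day 56 Visit to be one month after dosing.

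**Sensitivity to the last dose.** Section 13.6.3 describes dosing "once every evening for 28 days", which could be read as a last dose on Day 28. The count becomes 28 + *m* − 52 = *m* − 24, which is 4, 5, 6 or 7 of 9. If dosing ran to Day 31, the evening before the latest permitted Day 28 Visit, the count would be *m* − 21, capped at 9: 7, 8, 9 or 9. The planned schedule does not provide for Day 31 dosing, so I place no weight on that case.

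The two end points can also separate in the other direction. Section 7.6 lets a subject stop the drug and stay in follow-up. As an illustration, with a last dose on Day 10 and a 30-day month, the interval ends on Day 40, and the visit comes 52 − 40 = 12 to 60 − 40 = 20 days later.

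**The later end in Section 12.7.1.** Day 84 is 84 − 56 = 28 days after the nominal Day 56 Visit and 84 − 27 = 57 days after the last planned dose.

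**The case against.** The strongest reply is that the sentence in Section 12.7.2 already counts from the final application. On this view the parenthesis is a reminder of roughly when that falls, and on the nominal schedule it is right to within a day or two. The sentence in Section 12.7.1 can be read as an addition: a woman who continues to Day 84 has also met the Section 12.7.2 requirement on the planned schedule. No pregnant or nursing woman can properly be enrolled, so naming them in Section 12.7.2 has no practical effect.

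Much of this stands. The nominal agreement is real, the shortfall is a matter of days, and the Section 12.7.1 sentence applies only to subjects whose sexual activity or partner changes during the study. The mention of pregnant and nursing women is a drafting slip.

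It does not rescue the parenthesis. That text presents the visit as equivalent to the interval, and a site following it within the permitted window can release a subject early. Nor does reading the two sections as cumulative remove the problem that one group has a different stated end which Section 12.7.2 does not mention.

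A reader might infer more than the documents support:

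- *That women face three different end times depending on the sentence read.* Only two sentences set an end time. Two of the three end points share one sentence and nearly coincide on the nominal schedule.
- *That five of nine visit days fail as a matter of fact.* That count needs a 30-day month, which the protocol does not state for contraception. Its fifth day is the nominal Day 56 itself, which the sentence names as the end.
- *That any two women with the same exposure can be given dates 28 days apart.* The later date applies only to the Section 12.7.1 subset.
- *That the consent form repeats the problem.* Consent pages are not among the documents reviewed, so this cannot be checked.

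**Conclusion.** Wrong as written, and small in size. The visit named as the end of the requirement can fall 25 days after the last planned dose, which is short of one month on any reading from 28 to 31 days. With a last dose on Day 27, 3 to 6 of the 9 permitted visit days are too early, depending on the assumed length of a month, and the largest shortfall is 3 to 6 days. Separately, the subset described in Section 12.7.1 has a stated end nominally 28 days later than the Day 56 Visit.

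These figures rest on dosing that ends on Day 27 as planned and on the assumed month lengths. The documents do not say how many enrolled women would be of childbearing potential, so the number affected cannot be estimated. No endpoint, sample size, power or significance level is touched.

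The SAP (Section 5.6.2.2) records that the end-of-study visit was Day 56 under the first protocol version and Amendment 1, and became Day 84 under Amendment 2. The two sections may therefore have agreed nominally until the study was lengthened. That is an inference about origin and does not settle which end was intended.

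**What to change.** Reconcile Sections 12.7.1 and 12.7.2 with the Day 56 Visit window in Table 5 and Section 12.4.3. The end of the requirement for women should be stated once and in the same words wherever it appears. If a visit is still named beside an interval, the text should make clear which governs, so that the visit cannot release a subject before the interval the sentence states. If a month remains the unit, give its length in days. If subjects whose circumstances change during the study are meant to have a different end, say so explicitly in Section 12.7.2.

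As a minor clean-up, reconcile the mention of nursing and pregnant women in Section 12.7.2 with Exclusion Criterion 3.

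Which end point or duration is right is for the sponsor's clinical team. The change is wording in the next protocol amendment, with a check that the consent text agrees. It needs no extra visits, tests or subjects and no change to the analysis.
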